Background PPI Use: Acid suppression therapy is commonly prescribed, particularly in the VA for symptomatic GERD relief. Our research team, which includes practicing clinicians and experienced GERD researchers (Drs. [name] and [name]) debated a design wherein we would require research subjects to discontinue all acid suppression therapy for the duration of the study. It is clear that based upon symptom burden and for the purposes of adherence to study procedure that this would not be feasible. Further, we were concerned that if acid related damage were occurring off of acid suppression, then such a design may not be ethical. Thus, we have adapted a much more "clinical" or "intention-to-treat" mindset to the study design. Indeed, in a clinical setting, patients are most often treated empirically. Thus, we will follow AGA guidelines⁹ and have subjects maintain acid suppression therapy during the intervention, with the exception of the 7-day period prior to impedance and manometry testing. To determine the effect of acid suppression on the hormonal milieu we will now draw blood pre and post medication discontinuation. The only potential confounder to this approach would be if the efficacy of the dietary intervention were dependent upon having a highly acid and refluxing esophageal environment. This does not seem biologically plausible, and additionally the efficacy of the dietary intervention to reduce GERD in our preliminary data was not acid dependent given that all subjects self-discontinued use of acid suppression medications. *We will perform secondary analysis in which changes in PPI use over time will be assessed. We will use the daily medication (type and dose) and diet checklist data and 24hr diet recall data to conduct secondary analyses and verify the assumptions of our primary model. Summary statistics by diet group will be calculated to determine if weight loss, PPI use, total CHO, and simple CHO are consistent with the study design. We will also use the linear mixed effects model to determine if total and simple CHO are associated with total percent time pH < 4 by replacing the indicator variables in the primary model with these continuous covariates and their interaction. A secondary analysis of changes in PPI use over time will be considered. For this analysis, we will use the daily medication checklist (type, amount and dose) to create continuous variables of the weekly dose of PPI. PPI dose will be the outcome in a linear mixed effects regression model that includes time modeled flexibly using restricted and diet group indicators. An analogous model using weight as the outcome will be estimated.*

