Diets: We have extensive experience designing, prescribing and assessing diets.^{42,43} At baseline, dietary intake will be assessed by the Vanderbilt Nutrition and Diet Assessment Core (full methods described under Measures below). Energy content of daily intake will be estimated based on the individual's daily energy requirement using the Harris Benedict Equation with an activity factor of 1.2.⁴⁴ By doing so, calorie level will be individualized to assure weight maintenance during the study. In addition to being weighed at each clinical testing visit, body composition will be evaluated via DEXA scans at clinical testing visit to assure no changes in either total fat or truncal fat mass influence study results.

Subjects will be provided with daily meal plans that adhere to the composition of the treatment arm to which the subject is randomized. Meal plans will be developed by the co-Investigator ([name]) using NDS-R software (NDS-R version 2013, Nutrition Coordinating Center, Minn, MN) and instructed to subjects by the study dietitian at the end of study week 1 (see Schema below). To manipulate the carbohydrate amount (high vs low), we will alter the fat content of the diet. There will be no difference among diets in protein content. To manipulate type of carbohydrate (complex vs simple), we will provide instructions, the written meal plan, and a comprehensive list of which carbohydrate foods the subject can/can't consume.

To clearly delineate, simple carbohydrates are defined as those carbohydrates classified as mono- or di-saccharides, meaning they have one (glucose, galactose, fructose) or two (sucrose, lactose, maltose, trehalose) sugar units. Major sources of simple carbohydrates (or "sugars") are: soft drinks, cakes, cookies, pies, fruit punch, sweet tea, candy, table sugar, and syrups. Complex carbohydrates are also known as "starches" and consist of the oligo- and poly-saccharides, meaning they have 3 or more sugar units. Major sources of complex carbohydrates (or "starches") are: grains, cereals, legumes, corn, popcorn, pasta, rice, potatoes and vegetables. We recognize that major sources of both simple and complex carbohydrates have components of both and we are able to quantify these within a food using the NDS-R software.

All meal plans will provide 3 meals and 2 snacks per day that meet the macronutrient composition and the diet treatment arm:

- HTHS Diet: 55% total CHO (½ complex / ½ simple CHO), 30% fat, 15% protein

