- HTLS Diet: 55% total CHO (85% complex / 15% simple CHO), 30% fat, 15% protein
- LTHS Diet: 35% total CHO (½ complex / ½ simple CHO), 50% fat, 15% protein
- LTLS Diet: 35% total CHO (85% complex / 15% simple CHO), 50% fat, 15% protein

Power Analysis and Sample Size: Our primary outcome is a continuous variable, percent time pH < 4.0 in the 24hr period. This is based on the clinical gold standard of pH < 4.0 for > 5.5% of the 24hr period. To determine sample size, we used data from 205 obese patients with chronic GERD from [name] clinic population. In this sample, the SD for percent time < pH was 9.8 and the interclass correlation was 0.39 ($\omega = \omega^2_b / (\omega^2_b + \omega^2_e)$). We used these values as inputs into a statistical simulation (10,000 replications) to determine the probability of detecting any treatment group effect using the linear mixed effects model. The following table presents the power of an overall (4 d.f.) test to detect various absolute changes in pH by diet groups ($\omega_1, \omega_2, \omega_3, \omega_4$). We assume $n_1=40$ subjects per group complete the entire study and $n_2=5$ or $n_2=3$ subjects per group complete 80% of the study before returning for pH testing. We use a two-sided significance level of 0.05.

Absolute effect size	3.7%, 3.7%, 3.7%, 3.7%	0%, 4.5%, 4.5%, 4.5%	0%, 4%, 4%, 4%	0%, 0%, 5%, 5%	0%, 0%, 0%, 7%
Power ($n_1=40, n_2=5$)	0.80	0.89	0.80	0.85	0.87
Power ($n_1=40, n_2=3$)	0.79	0.88	0.79	0.83	0.86

Power for different effect size scenarios that give 80%-90% power are presented in the table. If the absolute change in percent time pH < 4 for each of the four diet groups is 3.7%, we will have 80% power to detect any effect of diet. If 1 diet group is not effective and the other groups have a 4.5% effect, we have almost 90% power to detect a diet effect. In our pilot data, the 25th/50th/75th percentiles of percent time pH < 4 were 4.8%/8.5%/12.4%. Thus, a 3.7% decrease is a change from the median to 25th percentile, a 4% decrease is a change from the 75th percentile to the median, a 5% decrease is a change from the 80th percentile to the median, and a 7.6% decrease is a change from the 75th to the 25th percentile. The standard error for any pairwise comparison between groups will be 1.9% under all scenarios ($n_1=40$ and $n_2=3$ or $n_2=5$).

2.3 SPECIFIC AIMS:

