Aim 1: *To determine effects of dietary carbohydrate consumed (amount and type) on percent time with esophageal pH < 4.0, as well as number of reflux episodes, GERD symptoms and GERD medication use, in 200 obese veterans who have chronic high frequency of GERD symptoms.* To meet this aim we will use a randomized controlled trial in which we manipulate amount of total and simple dietary carbohydrate intake for duration of 9 weeks.

Aim 2: To assess associations between GERD resolution variables and factors related to potential mechanisms by which modifying dietary carbohydrate intake could resolve/reduce GERD in obese veterans.

2a: We will investigate associations related to whether the effect is nutritionally mediated by measuring change in dietary fiber load and dietary glycemic load, and thus, whether these changes are related to improved gastric acid secretion (% time pH < 4), gastric motility, and/or the other parameters that comprise the Johnson-DeMeester score.

2b: We will also investigate whether effects are associated with changes in the hormonal milieu by measuring hormonal response of gastrin, glucagon, GLP-1, ghrelin and insulin, which could potentially influence gastric acid secretion, gastric motility and/or lower esophageal sphincter function.

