6.0 Study Procedures

Randomization: 200 subjects (50 per arm) will be randomized to diet treatment arm. we have reviewed drop-out rate from clinical trials in gastroenterology in this population ([name] and [name] personal communications), which would predict a 20% drop out rate. The number of subjects to enroll reflects a completion rate of 80% (enroll 50 per arm = 200 subjects x 0.80 = 160 completers). In considering that drop out could be higher, we will now include subjects in our final analyses who notify us they are dropping-out between weeks 7-9 by asking them to return for a final visit at the time of drop-out (we do this regularly and get agreement from about 66% of subjects to return for a final testing session even if they are not continuing to wk 9). Randomization of subjects will be carried out using unified reproducible methods (i.e. saved random number seed) provided by the Biostatistician ([name]). We will use a permuted block randomization scheme, stratifying on gender to ensure this covariate is balanced

between randomization groups. The block size will be varied randomly. Treatment assignments will be contained in sealed, thick envelopes to be opened after informed consent is obtained.

Overall Schema:

Timepoint	Baseline	Day 1-7	End Wk 1	Day 8-57	Day 57-63	End Wk 9
Consent & Enrollment	X					
Randomization			X			
Bloodwork	X		X		X	X
Diet Intervention						
Off PPIs #1						
Clinical Testing #1				X		
Off PPIs #2						
Clinical Testing #2						X

Testing Procedures:

Baseline levels of all measures listed below will be obtained prior to study day 1.

PPIs will be stopped for 1 week, medications that affect gastric motility for 2 days, H₂RAs for 2 days, and antacids for 2 days - *prior to testing on study days 7 and 63. Additional blood work will be drawn on study day 57 for evaluation of levels prior to discontinuation of PPIs #2.*

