analysis of only the complete cases would bias the results. *We will now request to subjects that inform of us they are dropping out between weeks 7 to 9 that they come in for a final visit. We have found that about 2/3 of subjects will agree to come in for a final visit even if they are not continuing to the end of study (week 9). This will significantly reduce the potential for missing data.* We will also attempt to obtain the specific reason for dropout on a case by case basis. Indirect information about the nonrandom dropouts will be obtained by using binary logistic models to predict the probability of dropping out using baseline variables. Thus, the impact of dropout on our results will be compared using assumptions that vary from missing completely at random to informative missing.

Sensitivity Analyses: We will use the daily diet data and daily medication checklist (type and amount) to conduct secondary analyses and verify the assumptions of our primary model. Summary statistics by diet group will be calculated to determine if weight loss, PPI use, total CHO, and simple CHO are consistent with the study design. We will also use the linear mixed effects model to determine if total and simple CHO are associated with total percent time < pH 4 by replacing the indicator variables in the primary model with these continuous covariates and their interaction. A secondary analysis of changes in PPI use over time will be considered. For this analysis, we will use the diary card data to create continuous variables of the weekly dose of PPI. PPI dose will be the outcome in a linear mixed effects regression model that includes time modeled flexibly using restricted and diet group indicators. An analogous model using weight as the outcome will be estimated. Our study is designed for subjects to maintain weight, but if weight loss differs by treatment arm, it may introduce confounding into our study. We will include weight loss as a covariate in our regression model to determine if our results are altered compared to the main analysis. This additional sensitivity analyses will be conducted as needed, for example where weight change is significantly different among groups, to assure effects are due to dietary not body weight change.

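### The only model planned for weekly PPI dose leaves out the baseline dose and gives no rule for the protocol PPI-off weeks, so it is valid but less precise than it could be

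*Combined protocol and SAP*

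**What the plan says.** Aim 1 (section 2.3) covers percent time with pH below 4 "as well as number of reflux episodes, GERD symptoms and GERD medication use, in 200 obese veterans". Medication use is therefore a named response.

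Its analysis appears twice in near-identical words, under Background PPI Use (section 2.1) and under Sensitivity Analyses (section 10.0). The status is modest: "A secondary analysis of changes in PPI use over time will be considered". Daily medication records become a weekly dose, and "PPI dose will be the outcome in a linear mixed effects regression model that includes time modeled flexibly using restricted and diet group indicators". A word seems to be missing after restricted. No other model for PPI dose is given, though summary statistics of PPI use by diet group are planned.

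The schedule matters here:

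- Subjects are to "have subjects maintain acid suppression therapy during the intervention, with the exception of the 7-day period prior to impedance and manometry testing" (section 2.1).
- Before testing on days 7 and 63, "PPIs will be stopped for 1 week, medications that affect gastric motility for 2 days, H₂RAs for 2 days, and antacids for 2 days" (section 6.0).
- Meal plans are "instructed to subjects by the study dietitian at the end of study week 1" (section 2.2).
- "Baseline levels of all measures listed below will be obtained prior to study day 1" (section 6.0), and Medication Use is one of the listed measures.

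For the primary outcome, section 10.0 does bring in the baseline value, with precision as the stated reason.

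**The concern.** Two things are left open in the only model for this response.

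First, the baseline dose. Subjects are likely to differ in how much PPI they take before the study. A random intercept accounts for the correlation of weeks within a subject, but the between-subject variance stays in the comparison of arms. A baseline covariate removes part of it. The only in-study week before the diet is week 1, and PPIs are stopped in that week. The on-PPI reference must therefore come from the record taken before day 1, which the model does not name.

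Second, the PPI-off weeks. The plan does not say whether they are dropped, set to missing, or counted as zero. Week 9 lies inside the diet period and is off PPI in every arm. Counting it as zero would shrink the reported diet coefficient.

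At stake are the precision and the scale of a secondary estimate for an Aim 1 response.

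**Working it through.** The plan states no SD, correlation or power for PPI dose, so there is no figure of its own to reproduce.

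**Weeks.** Days 1-7 are week 1 and days 57-63 are week 9; both are PPI-off. The diet starts after week 1, so the diet weeks are 2-9 (eight weeks), of which weeks 2-8 (seven weeks) are on PPI.

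**Baseline adjustment.** Assume total variance 1, the same correlation r between any two weekly doses (the baseline week included), and no missing weeks.

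- Variance of a subject's mean over seven weeks: V = r + (1 - r)/7.
- Covariance of that mean with the baseline dose: r.
- Variance left after adjustment: V - r².
- SE factor: sqrt(1 - r²/V).
- Unadjusted subjects per arm that match 40 adjusted ones (40 completers per arm is the section 2.2 assumption): 40/factor².

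| r | V | SE factor | Equivalent n per arm |
|---|---|---|---|
| 0.3 | 0.400 | sqrt(1 - 0.09/0.400) = 0.88 | 51.6 |
| 0.39 | 0.4771 | sqrt(1 - 0.1521/0.4771) = 0.83 | 58.7 |
| 0.5 | 0.5714 | sqrt(1 - 0.25/0.5714) = 0.75 | 71.1 |
| 0.8 | 0.8286 | sqrt(1 - 0.64/0.8286) = 0.48 | 175.8 |

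The row at 0.39 is for reference only. Section 2.2 says "the interclass correlation was 0.39" for percent time with pH below 4, which is a different variable. Simulation of 4,000 comparisons of 40 against 40 gave SE ratios of 0.886, 0.755 and 0.480 at r = 0.3, 0.5 and 0.8.

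**Week 9 as zero.** With diet main effects only, the coefficient is a difference of subject means. Adding a week that is zero for everyone multiplies every subject mean by 7/8 = 0.875. The estimate and its SE shrink together, so z does not change. The factor would be 7/9 = 0.778 only if week 1, which comes before randomisation and the diet, were also entered.

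**Mixed-model example.** Four arms of 40, a spline for week and a random intercept, with assumed SD 50, r = 0.5, and a true effect of -30 in one arm:

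| Model | Estimate (SE) | z |
|---|---|---|
| Weeks 2-8, named terms | -27.56 (8.40) | -3.283 |
| Weeks 2-9, week 9 = 0 | -24.12 (7.35) | -3.283 |
| Weeks 2-8, baseline covariate | -30.20 (6.15) | -4.912 |

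**Baseline as a time-0 response instead.** In the same example, a common baseline mean with a diet-by-post term gives z = -4.78 for weeks 2-8, close to the covariate model. Adding week 9 as zero moves the estimate from -30.22 to -26.42 and z to -4.45.

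With only the diet main effects that the plan names, a baseline row does not help. The arms do not differ at baseline in expectation, so the coefficient becomes 7/8 of the difference. At r = 0.5 the SE changes by sqrt(0.5625/0.5714) = 0.992, where 0.5625 = 0.5 + 0.5/8. Then z is multiplied by 0.875/0.992 = 0.88, a loss of about 12%.

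**The case against.** The strongest reply is that baseline may already be intended. The analysis concerns changes over time, which implies a starting value. The mixed model written out for the primary outcome treats baseline as a time-0 response with a common mean and multiplies the diet indicators by time. Built the same way, the PPI model would recover most of the precision (z of -4.78 against -4.912 in the example). This stands as a possibility. The text does not establish it, because the PPI sentence names no diet-by-time or diet-by-post term, and without one the baseline row dilutes the effect.

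Three further objections stand:

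- The size of the gain is assumed. It depends on the correlation, equal correlation across weeks, complete data, and a baseline record as reliable as a weekly log.
- Under the named terms, the week 9 issue only rescales one secondary coefficient.
- An average over weeks 2-8 is not the whole question if the effect builds up. Suppose it rises linearly from week 2 to week 9. The weeks 2-8 average is then 4/8 of the week 9 effect and 4/7 of the week 8 effect. This is a reason to report a diet-by-time term as well.

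A reader might infer that the planned analysis is biased towards an arm, or that the washout zeros cost power under the stated terms. The documents support neither. Randomisation balances baseline dose in expectation, the washout is the same in all arms, and z is identical with and without week 9 for completers.

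**Conclusion.** The point holds as a low-cost improvement to a secondary analysis. With the terms it names, the PPI-dose model is valid but less precise than the planned data allow. The SE could fall to about 0.88, 0.75 or 0.48 of its value at assumed intraclass correlations of 0.3, 0.5 or 0.8. Counting week 9 as zero would make the diet coefficient 12.5% too small as a measure of the on-PPI difference, with the test unchanged.

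These figures assume that the listed terms are the whole model, that washouts are followed, and that no weeks are missing. The exact 7/8 applies to completers. Subjects who leave in weeks 7-9 may be tested early, so a washout for them would fall in other weeks.

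It would go too far to call this a demonstrated loss of precision, since the documents give no correlation for PPI dose and the sentence is incomplete. Nor does it reach the main result: the primary pH outcome is measured off PPI. Confidence is medium.

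**What to change.** In sections 2.1 and 10.0, replace the PPI-dose sentence with wording such as:

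> Weekly PPI dose will be analysed in a linear mixed effects model with a subject random intercept, flexible time, diet group indicators, and the weekly PPI dose recorded before study day 1 as a covariate. Days in a protocol PPI-off period, set by each subject's own test dates, are excluded; weekly dose is the mean daily dose on the remaining days times 7. For subjects who complete the study, weeks 2-8 are analysed. A diet-by-time term will be reported as a supplement if change over time is of interest.

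Each diet coefficient is then the average on-PPI difference from the control diet.

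The cost is small: analysis wording, with no added visits. The baseline medication record must include PPI type and dose, and subjects not on a PPI enter with dose 0. The result speaks only to the weeks when PPIs were allowed.

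### Adjusting for weight loss measured after randomisation, at discretion and with a significant arm difference as the only named trigger, cannot show that the effect is dietary rather than weight-driven

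*Combined protocol and SAP*

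**What the plan says.** Section 10.0, Sensitivity Analyses, notes that the diets are meant to hold weight steady and that an arm difference in weight loss could introduce confounding. It continues: "We will include weight loss as a covariate in our regression model", so that the result can be compared with the main analysis. The next sentence makes this conditional on need: "for example where weight change is significantly different among groups, to assure effects are due to dietary not body weight change". No test, significance level, negligible difference in kg, or form for the weight-loss term is given.

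Other parts of the plan bear on the point:

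- The mixed model in section 10.0, Data Analysis, has a random intercept and four diet-by-time effects. It has no weight term.
- Summaries of weight loss by arm and a mixed model with weight as the outcome are planned with no trigger (section 10.0, Sensitivity Analyses; section 2.1, Background PPI Use).
- Energy prescriptions are individualised to maintain weight, and weight and DEXA are measured at the testing visits (section 2.1, Weight Loss; section 2.2, Diets).
- Section 1.5 lists better body weight among the predicted benefits of dietary intervention. Section 10.0, Interpretation, credits higher-fat, higher-protein eating with efficacy for weight loss.

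**The concern.** A confounder of a randomised comparison would have to precede randomisation. Weight change comes after it and, on the protocol's own account, may be caused by the diets. It is therefore a possible step on the path from diet to reflux. Two inferences then fail.

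1. **If the trigger stays silent.** Weight differences may be treated as absent when the test was merely too weak to find them.
2. **If the model is run.** Conditioning on weight loss gives a diet effect not passing through weight only when nothing unmeasured drives both weight change and acid exposure. Randomisation protects the comparison of arms but not the relation between weight change and reflux within arms. Adherence and medication use are obvious candidates for a shared cause, and the plan names none to be handled.

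At stake is the reading that carbohydrate acts independently of weight. Section 2.1, Weight Loss, makes that separation a design goal, and the end of section 10.0 presents benefit without weight loss as an important clinical advantage. This is the only planned analysis that compares the diet effect with and without weight in the model.

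**Working it through.** **Inputs from the plan.** Section 6.0: "200 subjects (50 per arm) will be randomized to diet treatment arm"; with 20% dropout, 50 × 0.80 = 40 per arm. Section 2.2: "We assume $n_1=40$ subjects per group complete the entire study". Also there: "We use a two-sided significance level of 0.05" and "In this sample, the SD for percent time < pH was 9.8 and the interclass correlation was 0.39".

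**Assumptions (not in the documents).** SD of weight change 3, 4 or 5 kg; the trigger is an overall four-arm test of weight change at the 0.05 level; illustrative correlations between weight change and acid exposure.

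**Step 1. The plan's own figures.** The plan gives no figure for weight. Its power table for the primary outcome can be checked. A 4 d.f. Wald test from the section 10.0 mixed model, with 40 + 5 per arm and 9.8 taken as the residual SD, gives 0.815/0.895/0.802/0.859/0.883 against the stated 0.80/0.89/0.80/0.85/0.87. With 9.8 as the total SD, power is 0.96 to 0.99 and the table does not reproduce. Both readings are carried into step 3.

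**Step 2. How often the trigger misses a real difference.** Power is from the non-central F with 3 and 4 × 40 − 4 = 156 d.f. (critical value 2.66). The non-centrality is λ = 40 × Σ(μ_g − μ̄)²/SD². For a difference d:

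- one arm differs from the other three: λ = 40 × 0.75 d²/SD²
- both low-total arms differ from the other two: λ = 40 × d²/SD²

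Example: d = 1, SD 3, one arm: λ = 40 × 0.75/9 = 3.33, power 0.30.

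| True difference | One arm differs: power at SD 3 / 4 / 5 | Two arms differ: power at SD 3 / 4 / 5 | Missed (range) |
|---|---|---|---|
| 1 kg | 0.30 / 0.18 / 0.13 | 0.39 / 0.23 / 0.16 | 61–87% |
| 2 kg | 0.87 / 0.61 / 0.41 | 0.95 / 0.75 / 0.54 | 5–59% |
| 3 kg | 1.00 / 0.94 / 0.78 | 1.00 / 0.98 / 0.90 | 0–22% |

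If each kg lost lowered percent time pH < 4 by 1 point (assumption), a missed 2 kg difference would carry 2 points, against the planned 3.7.

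**Step 3. What the adjustment does when there is a shared cause.** Suppose neither diet nor weight affects pH, the two low-total arms lose 2 kg more, and the SD of weight change is 4 kg. Let ρ be the correlation, from the unmeasured cause, between weight loss and lower acid exposure given arm and baseline. The adjusted diet effect is then biased by ρ × s/4 × 2, where s is the SD of week-9 percent time given baseline.

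- 9.8 as total SD: s = 9.8 × √(1 − 0.39²) = 9.02. Bias = 0.3 × 9.02/4 × 2 = 1.35 points at ρ = 0.3, and 2.26 at ρ = 0.5.
- 9.8 as residual SD: total SD = 9.8/√0.61 = 12.55 and s = 11.55. Bias = 1.73 and 2.89 points.

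Simulation on the first reading (3,000 trials, 40 per arm) agrees. At ρ = 0.3 the unadjusted effect is 0.0 with about 5% rejection, while the adjusted effect is 1.4 points with 10.5% rejection. At ρ = 0.5 the adjusted effect is 2.2 points with 27% rejection. At ρ = −0.3 it is −1.3, so the sign follows the unknown correlation.

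**Step 4. What happens without a shared cause.** With a true direct effect of −3 points, a 2 kg difference and 1 point per kg, the unadjusted effect is −5.04 and the adjusted effect −3.05. Here the planned adjustment works.

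**Step 5. Form of the covariate.** In the mixed model, diet acts only through products with time. A plain main effect of weight loss would shift baseline and week 9 equally, so it would not adjust the change at all in the intended way. The plan does not say which form is meant.

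**The case against.** The case on the other side is substantial.

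- **Significance is an example, not the sole condition.** A reader might infer that the model is run only after a significant test, or that the plan treats a non-significant one as proof of no weight effect. The text says neither. What stands is that the decision is left to data-dependent discretion and no other criterion is named.
- **Safeguards exist.** Weight-maintaining prescriptions, weighing, DEXA, summaries by arm and an untriggered weight model mean that an arm difference could be seen even if the adjustment were skipped. Section 1.3 also reports no large weight differences in the preliminary data. The diet-versus-weight reading therefore does not rest on the trigger or the adjustment alone.
- **The miss rates rest on an assumed SD.** This is correct, hence the range. A pairwise z-test of 1 kg with 40 per arm has power 0.32 at SD 3 kg and 0.61 at SD 2 kg, so no single figure should be quoted.
- **The practical error may be rare.** With differences of 1.5 to 2 kg and 1 to 1.5 points per kg, a silent trigger together with a significant, purely weight-driven primary result occurred in only 2–4% of simulated trials.
- **The bias needs a shared cause,** on which the documents are silent. This is also correct, but an analysis that depends on its absence should state that assumption.
- **Independence from weight is not an endpoint.** The aims do not list it. It is nevertheless a stated design goal and part of the planned interpretation.

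**Conclusion.** The point holds as a fault of interpretation and pre-specification. A silent weight test would not show equal weight change: under assumed SDs of 3 to 5 kg it misses 1 kg in 61–87% of trials and 2 kg in 5–59%, though 3 kg in only 0–22%. The adjusted model isolates a direct effect only if weight change and acid exposure share no unmeasured cause. With illustrative correlations of 0.3 to 0.5, a 2 kg difference and SD 4 kg, the bias is about 1.4 to 2.3 points on the total-SD reading, or 37% to 61% of the planned 3.7 points (1.35/3.7 and 2.26/3.7).

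A reader might infer that the primary result is biased, or that adjusting for weight is always wrong. The documents support neither: the primary model has no weight term, and step 4 shows the adjustment recovering the direct effect when its assumption is met. What fails is the claim that the analysis can *assure* a dietary cause.

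**What to change.** Amend section 10.0, Sensitivity Analyses, as follows.

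1. Run the weight-adjusted model in all cases and delete the significance trigger.
2. Report arm differences in weight change with confidence intervals, whatever their p-values.
3. Enter weight change at follow-up only: in the mixed model, as a product with time, so that it is zero at baseline. Include baseline weight and gender, and take account of baseline percent time pH < 4 (a covariate in the regression form; already the first outcome in the mixed model).
4. Label it a direct-effect (mediation) analysis. State that it assumes no unmeasured common cause of weight change and acid exposure, and show how the estimate moves over a range of correlations, as in step 3.
5. Keep the conclusion about diet on the unadjusted randomised contrast.
6. Replace the closing claim with wording such as: *to explore whether the diet effect is altered after accounting for weight change*.

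The data are already collected. The cost is SAP wording, one extra routine model with a short sensitivity calculation, and a more modest claim.
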